7.3.10 Visit V15 (week 72)

- Perform an abbreviated physical examination and record body weight
- Review SMBG and glycemic control record
- Measure vital signs, including blood pressures and heart rate
- Collect used study medications and dispense investigational products
- Draw blood if a minimum 10 h fast has been completed by the subject as described in [Section 6.9.2.1](#). The specific laboratory tests scheduled for this visit are listed in [Appendix 2](#).
- Collect a clean-catch, mid-stream urine sample
- Assess adverse events and potential DKA
- Record concomitant medications

7.3.11 Visit V16 (week 84, off-site phone visit)

- Review SMBG and glycemic control record
- Assess adverse events and potential DKA
- Record concomitant medications

7.3.12 Visit V17 (end of treatment, week 96)

- Complete EQ-5D-3L questionnaire
- Perform an abbreviated physical examination and record body weight
- Review SMBG and glycemic control record
- Measure vital signs, including blood pressures and heart rate
- Perform a 12-lead ECG measurement
- Draw blood if a minimum 10 h fast has been completed by the subject as described in [Section 6.9.2.1](#). The specific laboratory tests scheduled for this visit are listed in [Appendix 2](#).
- Collect a clean-catch, mid-stream urine sample.
- Collect used investigational products
- Assess adverse events and potential DKA
- Record concomitant medications

7.4 Visit V18 (Exit Visit or Early Termination Visit)

7.4.1 Visit V18 (week 98 or two weeks after the last dose of investigational product is administered or if a subject withdraws consent)

- Perform a complete physical examination and record body weight
- Review SMBG and glycemic control record
- Measure vital signs, including blood pressures and heart rate
- Draw blood if a minimum 10 h fast has been completed by the subject as described in [Section 6.9.2.1](#). The specific laboratory tests scheduled for this visit are listed in [Appendix 2](#).
- Collect a clean-catch, mid-stream urine sample
- Collect used investigational products if early termination
- Assess adverse events and potential DKA
- Record concomitant medications

7.5 Discontinuation of Investigational Product Administration

Subjects who discontinue the investigational product administration early but are willing to remain in the study to allow safety information to be collected should complete the End of Treatment visit procedures. Safety data may be documented following the scheduled clinic visit and/or phone interview procedures as much as possible without the study drug dispensation and accountability procedures. Alternative follow-up methods to allow safety assessment to be recorded may be implemented as unscheduled visits.

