6.16 Healthy-related Quality of Life Assessment

EQ-5D-3L is a multi-attribute utility instrument for measuring preferences associated with an individual's health state. The instrument includes a visual analog scale and a descriptive system with 5 dimensions (mobility, self-care, usual activity, pain/discomfort, anxiety/depression), each of which has 3 levels (no problem, some problem, extreme problem).

Enrolled subjects will complete the EQ-5D-3L questionnaire independently at clinic Visits V6, V11, V14 and V17. EQ-5D-3L should be completed prior to other scheduled procedures at those visits.

6.17 Removal of Subjects from the Trial or Discontinuation of Investigational Product Administration

The investigator must emphasize to potential subjects the importance of continued participation for the full duration of the trial during the informed consent process. Potential subjects should be informed that the trial procedures will allow additional medications to control hyperglycemia or other adverse conditions. It is also important to emphasize that missing data and missed visits could affect the entire trial. If subjects are dissatisfied with the conduct of the trial but have not withdrawn, the investigator should make an effort to address their concerns and retain them in the trial if possible. In doing so, investigators must be careful that the efforts do not cross over into coercion. Investigators should encourage a subject to remain in the study even if the investigational product administration is stopped so that safety information can be collected.

Participation in a clinical trial is voluntary. A subject can withdraw from the study at any time. The sponsor may terminate the study for medical or administrative reasons. An investigator may decline to participate in the conduct of the study if either the investigator or the Institutional Review Board (IRB)/Independent Ethics Committee (IEC) determines that, based on good medical judgment, immediate cessation is appropriate for subject safety. If a decision is made to withdraw a subject from the study, no further investigational product should be administered. Even if the subject discontinues study medication, every attempt should be made to complete all required study evaluations and procedures. Reasons for all withdrawals should be recorded on the CRF. Examples of reasons for withdrawal include:

1. A protocol violation has occurred,
2. A serious or intolerable adverse event has occurred,

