9.2 Determination of Sample Size

Approximate total 420 subjects will be randomized and equally allocated to receive bexagliflozin tablets 20 mg or placebo, and glimepiride capsules, 2 mg, 4 mg, 6 mg or placebo.

The sample size calculation for this study is based on a two group t-test with a one-sided significance at the 0.025 level and the following assumptions:

1. The non-inferiority limit (margin) for mean change from baseline to week 60 in HbA1c comparing bexagliflozin group to glimepiride group will be 0.35%

2. The pooled standard deviation for the change from baseline to week 60 in HbA1c for bexagliflozin group and glimepiride group will be 1.0%

Under the above assumptions, an estimated sample size of 172 patients is needed in each treatment arm to detect non-inferiority of bexagliflozin to glimepiride with respect to change in HbA1c at week 60 from baseline. This estimation is based on a one-sided t-test with 90% power at a 0.025 level of significance. A sample size of 210 per arm has been selected to account for approximate 18% drop-out rate and to allow adequate safety evaluation. The total sample size for this study will be 420 subjects.

This study will be conducted at multiple investigative sites and will likely involve various numbers of subjects at each site. Enrollment will be on a competitive basis, but will be capped at 40 subjects from each site.

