8.1.1. Primary Efficacy Analysis

Let $\mu_{\text{bexagliflozin}}$ and $\mu_{\text{glimepiride}}$ represent the mean changes from baseline in HbA_{1c} at Week 60 for bexagliflozin and comparator groups, respectively. The following hypotheses will be tested:

$$H_0: \mu_{\text{bexagliflozin}} - \mu_{\text{glimepiride}} > \delta \text{ versus}$$

$$H_1: \mu_{\text{bexagliflozin}} - \mu_{\text{glimepiride}} \leq \delta$$

Non-inferiority margin δ is chosen to be 0.35% using clinical judgment, with reference to relevant regulatory guidance, and justified by published glimepiride efficacy study (Charpentier et al. 2001).

This hypothesis will be tested based on ITT analysis set. Missing data will be imputed via multiple imputations, following which the MMRM will be repeated on the complete datasets with results combined across complete datasets using standard multiple imputations techniques; HbA_{1c} values collected after the start of rescue medication will not be excluded. A pattern-mixture model will be used to explore the impact of the missing data. Imputation will be conducted within each treatment arm and subgroup (treatment completer vs. treatment terminated early) under the assumption that non-adherent subjects with missing data will follow the same trajectory of non-adherent subjects with values observed. All efforts will be made to retain subjects in the study. If treatment is discontinued, subjects are encouraged to remain in the study and complete all scheduled visits, including final follow-up visit. However, with all efforts, insufficient values may be available for reliable imputation. This analysis will be performed only if $\geq 3\%$ (approximately 6) of subjects in each treatment arm completed scheduled week 60 visit after treatment is stopped. This number is chosen to allow sufficient data to establish a regression model for imputation. For this analysis, the following three-step approach outlined below will be used:

1. Non-monotone (intermediate visits) missing data will be imputed first using the Monte Carlo Markov Chain (MCMC) method under the MAR assumption in all

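### Protocol 7.5 makes follow-up after stopping drug optional and safety-framed, although the SAP's primary analysis depends on week-60 HbA1c from those same subjects

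*Protocol*

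**What the plan says.** **Protocol 7.5** is the section written for subjects who stop drug and stay. It says that those "willing to remain in the study to allow safety information to be collected should complete the End of Treatment visit procedures". After that visit, safety data *may* be recorded, using scheduled clinic or phone procedures as far as possible and leaving out drug dispensation and accountability. Unscheduled contacts are an accepted alternative. HbA1c and week 60 are not mentioned.

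**Protocol 6.17** contains two sentences that pull in different directions. One gives the reason for retention: "Investigators should encourage a subject to remain in the study even if the investigational product administration is stopped so that safety information can be collected". The other says that, even off study medication, "every attempt should be made to complete all required study evaluations and procedures".

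**SAP 8.1.1** imputes missing HbA1c within arm and by whether treatment was completed, so that subjects off drug are imputed from subjects off drug who were observed. This primary analysis runs only if at least 3%, given as approximately 6, "of subjects in each treatment arm completed scheduled week 60 visit after treatment is stopped". If too few values exist, the MMRM on all available data is used. The same section says that subjects who stop are encouraged to complete all scheduled visits. SAP 13 records that the retrieved-dropout analysis was introduced in the SAP, to be used if the data allow, in place of the protocol's available-data MMRM.

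**Protocol Appendices 1 and 2** already schedule HbA1c, body weight and vital signs at Visit V14 (week 60).

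**The concern.** The SAP's primary estimator needs one specific measurement from one specific group: week-60 HbA1c in subjects no longer taking drug. The protocol section that sites would consult for exactly that group gives safety as the reason for staying and makes later contacts optional.

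An End of Treatment visit held when drug is stopped does include an HbA1c. Under the windows in SAP 6.4, though, it counts as week 60 only if it falls on days 378 to 461. Someone who stops at week 20 and is then followed by phone supplies no week-60 value.

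The protocol can be firm about follow-up when it means to be. Section 6.14.13 requires follow-up for cardiovascular events for the whole study even after permanent withdrawal of study medication. There is no equally explicit rule for HbA1c.

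At stake is which primary analysis is run. If site practice follows the permissive reading, the trial is likely to end on the fallback, which assumes missingness at random. The week-60 weight and blood pressure endpoints would lose data in the same way.

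**Working it through.** **1. The plan's own sample size.** Inputs from Protocol 9.2: "The non-inferiority limit (margin) for mean change from baseline to week 60 in HbA1c comparing bexagliflozin group to glimepiride group will be 0.35" (per cent); "The pooled standard deviation for the change from baseline to week 60 in HbA1c for bexagliflozin group and glimepiride group will be 1.0" (per cent); "This estimation is based on a one-sided t-test with 90% power at a 0.025 level of significance"; true difference taken as zero.

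n per arm = 2 × (1.960 + 1.282)² × 1.0² / 0.35² = 2 × 10.51 / 0.1225 = 171.6, so 172. A noncentral-t check at 172 gives power 0.899.

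Inflation: 172 / (1 − 0.18) = 209.8, so 210 per arm. Both figures reproduce. Collecting more week-60 values off drug does not change them.

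**2. The threshold.** 0.03 × 210 = 6.3. Six subjects are 6/210 = 2.86% and seven are 7/210 = 3.33%. The SAP's approximate figure is 6; a strict reading of at least 3% needs 7.

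**3. Share of stoppers who must be retrieved.** Let d be the proportion of an arm that stops drug before week 60. The documents give no value for subjects who stop drug but stay in the study. The 18% dropout rate is used as a stand-in, with a range around it. Required share = k / (210 × d).

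| d (assumed) | Stoppers per arm | k = 6 | k = 7 |
|---|---|---|---|
| 10% | 21.0 | 28.6% | 33.3% |
| 18% | 37.8 | 15.9% | 18.5% |
| 25% | 52.5 | 11.4% | 13.3% |

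**4. Chance that both arms qualify.** Let r be the share of stoppers with a week-60 value, also an assumption. With independent arms and equal rates, the probability is [Pr(Binomial(210, d × r) ≥ k)]².

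| r | d = 10%, k = 6 | d = 18%, k = 6 | d = 18%, k = 7 | d = 25%, k = 6 |
|---|---|---|---|---|
| 10% | 0.000 | 0.032 | 0.008 | 0.183 |
| 15% | 0.010 | 0.252 | 0.116 | 0.644 |
| 20% | 0.060 | 0.593 | 0.402 | 0.909 |
| 25% | 0.183 | 0.835 | 0.701 | 0.983 |
| 30% | 0.365 | 0.946 | 0.882 | 0.998 |
| 50% | 0.909 | 1.000 | 0.999 | 1.000 |

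At d = 18%, moving from 10% to 30% retrieval takes the primary analysis from very unlikely to very likely to run. Follow-up wording can plausibly affect retrieval over a range of that kind.

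**5. The threshold is a floor.** At week 60 the imputation regression in SAP 8.1.1 uses region (two levels, SAP 6.5), treatment background, eGFR category, baseline HbA1c and HbA1c at weeks 12, 24, 36 and 48. That is 8 slopes plus an intercept, or 9 coefficients, against 6 or 7 observed subjects at the minimum. Retrieval well above the threshold is therefore worth having.

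**The case against.** A reader might infer that the protocol tells sites to collect safety data only. It does not. No passage says so or tells sites to omit HbA1c. Section 6.17 asks for every attempt at all required evaluations and stresses the harm done by missed visits. Section 7.5 itself points to scheduled-visit procedures and removes only the drug-handling steps. Protocol 9.8 counts glycemic control parameters, vital signs and physical examination results as safety data, so even a narrow safety reading can include HbA1c, blood pressure and weight. The SAP encourages stoppers to attend all scheduled visits.

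The SAP also foresees sparse retrieval. It sets a threshold, pre-specifies a fallback close to the protocol's own primary MMRM (Protocol 9.5.2), and plans a tipping-point analysis over 25 combinations (SAP 8.1.2). The trial is never without a primary analysis.

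Finally, 18% is described as a dropout, early termination or early withdrawal rate. It includes people who leave the study, whom no wording in 7.5 can retrieve.

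All of this stands, and it narrows the point to an inconsistency. It does not remove it: in the section addressed to these subjects, later documentation is optional, a phone contact is enough, and week-60 HbA1c is not required.

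**Conclusion.** The point holds as a mismatch between Protocol 7.5 on one side and Protocol 6.17 and SAP 8.1.1 on the other. The section that sites would follow is the weakest of the three, and it bears on data that decide whether the planned primary analysis runs. Between 6 and 7 off-drug week-60 values are needed in each arm. That is 16–19% of stoppers if 18% stop and 29–33% if 10% stop. Both stopping rates are assumptions, as are the retrieval rates and the independence and equality of the arms.

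A reader might go further and multiply 18% by the 0.79% effect in Protocol 3.2.3 to get 0.14%, about 40% of the 0.35% margin, as the bias of the fallback. The documents do not support that. The 0.79% is a week-24 placebo comparison from another study. The product is a maximum for a single arm, set against a between-arm margin. Stopping would affect both arms and could largely cancel. The MMRM also conditions on whatever values each subject has. Neither the direction nor the size of any bias in the treatment difference can be derived from the documents.

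**What to change.** Reconcile Protocol 7.5 with Protocol 6.17 and SAP 8.1.1. In 7.5, and in the retention sentence of 6.17, state that subjects who stop investigational product but remain in the study continue the scheduled visits in Appendices 1 and 2. Name HbA1c, body weight and blood pressure at week 60 and through week 96, and exclude only drug dispensation and accountability.

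This is a wording change. It adds no visit type or test and leaves the sample size and treatment rules alone. The cost is some additional scheduled visits and blood draws in subjects who are off drug. It cannot recover data from subjects who withdraw from the study altogether.

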7.6 Early Termination Procedures

Subjects who withdraw consent and have received investigational products should have a follow-up examination, including a complete physical examination, vital signs, ECG, and

clinical laboratory tests (hematology, serum chemistry, and glycemic control). The sponsor must be notified in the event that a subject withdraws or has been withdrawn from the study.

8 QUALITY CONTROL AND ASSURANCE

The clinical research facility will be monitored by the study monitor to ensure correct performance of the study procedures and to ensure that the study is conducted according to the protocol and relevant regulatory requirements. CRF entries will be verified with the source documentation.

Quality control principles will be applied throughout the performance of this study by following the Standard Operating Procedures (SOPs) of the contract research organization (CRO) and the sponsor. Review procedures will be implemented at the CRO for all documents that are generated in relation to the study.

9 PLANNED STATISTICAL METHODS

9.1 General Considerations

The following sections provide a summary of the planned analysis of the trial but a complete statistical analysis plan will be developed as a separate document and will be the final plan. All statistical analyses will be performed using SAS Version 9.2 or higher.

In general, descriptive statistics (number of subjects [N], mean, standard deviation [SD], Q1, median, Q3, minimum and maximum) will be presented for continuous variables, and frequency and percentage for categorical variables.

The primary efficacy non-inferiority test will be one-sided at 0.025 significance level. The upper bound of the 95% confidence interval (CI) on the difference of HbA1c reduction between bexagliflozin and glimepiride will be used to determine the study's conclusion. That is, if the upper bound of the CI is within 0.35%, then the primary objective of the study is met. Superiority will be declared without additional statistical testing when the upper bound of the 95% CI for the difference in change from baseline at week 60 in HbA1c comparing bexagliflozin group with glimepiride group is less than 0.

The secondary efficacy objectives will be tested at two-sided 0.05 significance level following a sequential testing procedure to control the overall type I error of 0.05. The secondary efficacy endpoints will be tested only if the primary efficacy assessment achieves significance, and following the hierarchy as below:

1. Superiority test of the change in body weight in subjects with baseline BMI ≥ 25 kg/m² in the bexagliflozin group compared with glimepiride group at week 60
2. Superiority test of the change in SBP in subjects with baseline SBP ≥ 140 mmHg in the bexagliflozin group compared with glimepiride group at week 60
3. Superiority test of the difference in proportion of subjects with ≥ 1 severe or documented symptomatic hypoglycemia events in the bexagliflozin group compared with glimepiride group over 96 weeks

The exploratory efficacy objectives and safety objectives will be analyzed descriptively.

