- Adverse events, including adverse events of special interest (genital and urinary tract infections, diuretic effects, hepatotoxicity, MACE, hypoglycemia, fractures, malignancy, hypersensitivity reactions, hypotensive episodes, acid-base disorders, and renal failure events)
- Laboratory testing, including hematology, serum chemistry, and urinalysis
- Physical examination
- 12-lead ECG
- Vital signs
- Concomitant medication use

Other Assessment:

Health-related quality of life instrument EQ-5D-3L

Statistical Methods:

The primary hypothesis is that bexagliflozin is non-inferior to glimepiride by evaluating the treatment effect on HbA1c reduction at week 60 in combination with metformin. The non-inferiority margin for mean change from baseline at week 60 in HbA1c comparing bexagliflozin group with glimepiride group will be 0.35%. Superiority will be declared without additional statistical testing when the upper bound of the 95% CI for difference in change from baseline at week 60 in HbA1c comparing bexagliflozin group with glimepiride group is less than 0. The treatment difference will be examined by using a mixed model repeated measures (MMRM) analysis of covariance model (ANCOVA). The model will include treatment, visit, treatment-by-visit interaction and randomization stratification factors as the fixed effects terms and the baseline HbA1c value as a fixed effect covariate. Least squares mean treatment differences between the bexagliflozin group and the comparator group at week 60 in change from baseline will be estimated from the model. An unstructured covariance will be used to model the within-subject correlation. If the model with the unstructured covariance structure does not converge, an autoregressive(1) covariance structure will be used. HbA1c values obtained after the start of rescue medication will not be excluded from this primary analysis. Primary endpoint will be analyzed on both intention-to-treat (ITT) and per protocol (PP) analysis sets.

The MMRM model is one approach to obtain treatment effect estimates in the presence of missing data. As sensitivity analyses for missing data, the following will be performed on both ITT and PP analysis sets:

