1. Missing data will be imputed via multiple imputations, following which the MMRM will be repeated on the complete datasets with results combined across complete datasets using standard multiple imputation techniques; HbA1c values collected after the start of rescue medication will not be excluded.
2. Missing data will be imputed via LOCF, following which the MMRM will be repeated; HbA1c values collected after the start of rescue medication will be considered missing.
3. HbA1c values collected after the start of rescue medication will be considered missing,

and the MMRM analyses will be re-performed.

The effects of bexagliflozin on the changes from baseline at week 60 in body weight and systolic blood pressure, the difference in the proportion of subjects with ≥ 1 severe or documented symptomatic hypoglycemia events over 96 weeks and the change in HbA1c from baseline at week 60 will be tested as key secondary endpoints and will be analyzed in a hierarchical testing strategy and only if the primary objective is met. Similar to the primary endpoint, ANCOVA models will be used for the continuous secondary endpoints and logistic regression model will be used for the binary endpoint. A hierarchical testing strategy will be followed to preserve experiment-wide alpha at 0.05:

1. Superiority test of the change in body weight in subjects with baseline BMI ≥ 25 kg/m² in the bexagliflozin group vs. the glimepiride group at week 60
2. Superiority test of the change in systolic blood pressure (SBP) in subjects with baseline SBP ≥ 140 mmHg in the bexagliflozin group vs. the glimepiride group at week 60
3. Superiority test of the difference in proportion of subjects with ≥ 1 severe or documented symptomatic hypoglycemia event in the bexagliflozin group vs. the glimepiride group over 96 weeks

Additional effects of bexagliflozin versus glimepiride on the changes in HbA1c, FPG, SBP, body weight, the proportion of subjects who reach an HbA1c $< 7\%$, and the proportion of subjects with ≥ 1 severe or documented symptomatic hypoglycemia events over time, as well as the general safety in subjects with T2DM, will be analyzed as exploratory efficacy endpoints. These endpoints are considered exploratory and will not be adjusted for multiplicity.

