8.2. SECONDARY EFFICACY ENDPOINT(S) AND ANALYSES

The secondary endpoints will only be tested when the non-inferiority of the primary efficacy assessment is established at one-sided significance level of 0.025. To control the overall type I error of 0.05, the secondary efficacy objectives will be tested at one-sided 0.025 significance level following the sequence below:

- Superiority test of the change in body weight in subjects with baseline body mass index (BMI) ≥ 25 kg/m² at week 60.
- Superiority test of the change in SBP in subjects with baseline SBP ≥ 140 mmHg from baseline at week 60.
- Superiority test of the difference in proportion of subjects with ≥ 1 severe or documented symptomatic hypoglycemia events over 96 weeks

Analysis for secondary endpoints will be based on ITT analysis set and repeated for PP analysis set. For body weight and SBP, all post-baseline values up to week 60 will be used for model analysis. All values will be summarized.

8.2.1. Change in body weight in subjects with baseline body mass index (BMI) ≥ 25 kg/m² at week 60

This will be tested if the non-inferiority of HbA_{1c} and the previous secondary efficacy endpoints are significant. Data after rescue medication will not be excluded. The comparison of change in body weight between randomized treatments at week 60 will be carried out using the similar MMRM model as section 8.1.1 using all available data. The model will include terms for region, treatment, baseline HbA_{1c} as continuous variable, treatment background (metformin-only or metformin-and-OHA), and baseline eGFR (≥ 90 or < 90 mL/min/1.73 m²) as fixed effects and the corresponding baseline weight value as covariate. Treatment comparison p-values and difference at week 60 will be estimated from the model, with the two-sided 95 % CIs of the treatment difference also presented. If the superiority of HbA_{1c} is not established, the nominal p-value will not be used for inferential purposes. Summary table will be presented and figures will be displayed for ITT population.

8.2.2. Change in SBP in subjects with baseline SBP ≥ 140 mmHg from baseline at week 60

This will be tested if the change from baseline body weight is significantly different between bexagliflozin and glimepiride groups based on ITT analysis set for subjects with a BMI ≥ 25 kg/m². Change from baseline in SBP at week 60 will be analyzed in a similar manner as change in body weight, Section 8.2.1, based on ITT analysis set for all

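### HbA1c superiority is a key secondary with no stated place in the testing order, and SAP 8.2 and 8.2.1 disagree on whether body weight needs it

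*Protocol*

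**What the plan says.** HbA1c superiority at week 60 is the fourth key secondary objective (Protocol synopsis and 2.2; SAP 3.2), and HbA1c change is the fourth secondary endpoint (synopsis; SAP 4.2). The documents then treat it in four ways.

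- **Read from the primary interval.** Protocol 9.1: "Superiority will be declared without additional statistical testing when the upper bound of the 95% CI for the difference in change from baseline" is below 0. The synopsis repeats this almost word for word ("Superiority will be declared without additional statistical testing when the upper bound of the 95% CI for difference in change from baseline"). Protocol 9.5.2 and SAP 8.1.1 give the same upper-bound rule.
- **Part of the hierarchy.** The synopsis names HbA1c change, after weight, systolic blood pressure (SBP) and hypoglycemia, among the endpoints that "will be tested as key secondary endpoints and will be analyzed in a hierarchical testing strategy and only if the primary objective is met". It gives the purpose: "A hierarchical testing strategy will be followed to preserve experiment-wide alpha at 0.05".
- **Absent from every sequence.** The numbered list in the synopsis, the list in Protocol 9.1 and the list in SAP 8.2 all run weight, SBP, hypoglycemia and stop. Protocol 9.6 likewise applies the hierarchy to three endpoints. Protocol 9.1 and SAP 8.2 open the sequence on the primary result alone; SAP 8.2 adds that "the secondary efficacy objectives will be tested at one-sided 0.025 significance level following the sequence below".
- **A gate before weight.** SAP 8.2.1 tests weight only if non-inferiority "and the previous secondary efficacy endpoints are significant", although weight is first in the list just above it. It then says: "If the superiority of HbA_{1c} is not established, the nominal p-value will not be used for inferential purposes".

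SAP 13, which records departures from the protocol, covers covariates and missing-data handling but not the testing order.

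**The concern.** A fixed-sequence procedure controls error only if the sequence is fixed. Here the position of one confirmatory hypothesis is open, and with it the condition that opens the first step of the list. Does body weight open on non-inferiority or on HbA1c superiority?

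Suppose non-inferiority is met, weight favours bexagliflozin, and the HbA1c upper bound lies between 0 and 0.35. Under SAP 8.2 weight is a confirmed claim and SBP is tested next. Under SAP 8.2.1 the weight p-value carries no inference, and the two endpoints behind it fall too. That is an ordinary outcome for a trial sized for non-inferiority, and a choice between the two sections made after unblinding would be data-dependent.

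If superiority is instead kept outside the sequence while weight opens on non-inferiority, two branches each spend the full level.

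A smaller gap: SAP 8.2.2 opens SBP on weight without naming a direction ("This will be tested if the change from baseline body weight is significantly different between bexagliflozin and glimepiride groups").

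**Working it through.** **Inputs.** From Protocol 9.2 and SAP 3.8: margin 0.35, SD 1.0, one-sided 0.025, 90% power, 172 evaluable and 210 randomized per arm, 18% dropout. Assumed, because the documents give none: the true HbA1c and weight differences, and the correlation ρ between the two test statistics. Differences are bexagliflozin minus glimepiride, so negative is favourable.

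**The plan's own figure.** n = 2(1.960 + 1.282)² × 1.0² / 0.35² = 171.6, so 172 per arm; 172/0.82 = 209.8, so 210. The stated sample size reproduces at a true difference of 0.

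**Standard error and non-inferiority.** SE = 1.0 × √(2/172) = 0.1078. Non-inferiority is met when Z_H < 0.35/0.1078 − 1.96 = 1.286, which has probability 0.9007 at a true difference of 0.

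**Reading A: superiority outside the sequence, weight opens on non-inferiority.** With true HbA1c and weight differences both 0,

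P(at least one false favourable claim) = P(Z_H < −1.96) + P(−1.96 < Z_H < 1.286 and Z_W < −1.96).

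At ρ = 0 this is 0.025 + (0.9007 − 0.025) × 0.025 = 0.0469. From the bivariate normal for other ρ:

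| ρ | −0.7 | −0.5 | −0.3 | 0 | 0.2 | 0.5 | 0.7 | 0.9 |
|---|---|---|---|---|---|---|---|---|
| error | 0.0331 | 0.0388 | 0.0432 | 0.0469 | 0.0475 | 0.0453 | 0.0417 | 0.0352 |

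Simulation with 4 million draws per correlation agrees closely (0.0469 at ρ = 0). With 210 per arm and no dropout, non-inferiority power is 0.948 and the error at ρ = 0 is 0.0481. If non-inferiority were certain, the value at ρ = 0 would be 1 − 0.975² = 0.0494.

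**Reading B: HbA1c superiority gates weight.** Under the same null the error is P(Z_H < −1.96) = 0.025, so there is no inflation. The chance that weight can be tested at all, by true HbA1c difference d:

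| d | 0 | −0.1 | −0.2 | −0.3 | −0.4 |
|---|---|---|---|---|---|
| superiority gate, Φ(−d/0.1078 − 1.96) | 0.025 | 0.151 | 0.458 | 0.794 | 0.960 |
| non-inferiority gate, Φ((0.35 − d)/0.1078 − 1.96) | 0.901 | 0.987 | 0.999 | >0.999 | >0.999 |

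**Reading C: superiority last, after hypoglycemia.** Under the same null the error is P(non-inferiority met and Z_W < −1.96): 0.0081 at ρ = −0.7, 0.0225 at ρ = 0 and 0.0250 at ρ = 0.9. It does not exceed 0.025.

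**The case against.** The strongest reply is that the order is nearly settled. The synopsis list, Protocol 9.1, Protocol 9.6 and SAP 8.2 agree on weight, SBP, hypoglycemia, and Protocol 9.1 and SAP 8.2 open that chain on the primary result. The contrary text is two phrases in SAP 8.2.1, one of which refers to earlier secondary endpoints that do not exist for the first in the list. That looks like carried-over text. The synopsis sentence and the objective lists also name HbA1c superiority fourth, which suggests last place. All of this is fair, and it makes one resolution more natural. It does not remove the conflict: SAP 8.2.1 is operative as written, the SAP is declared the final plan, and the contradiction lies inside the SAP. Being named fourth in prose is not a testing rank while the upper-bound rule lets superiority be declared at any time.

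A second reply is that moving from non-inferiority to superiority on one interval costs no alpha. That is true of the step alone. It does not cover a second chain run at full level beside it.

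A third is that 0.0475 is below the stated overall 0.05. Literally so. But SAP 8.2 itself translates that 0.05 into one-sided 0.025 tests, so 0.025 is the fair comparison for favourable claims.

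The gate probabilities use an unadjusted two-sample SE, whereas the planned model is a baseline-adjusted repeated-measures analysis, so they are illustrative. The direction point on SAP 8.2.2 is minor, because the SAP 8.2 lead-in is already one-sided. Two-sided 0.05 in Protocol 9.1 and one-sided 0.025 in SAP 8.2 set the same threshold for a favourable claim.

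**Conclusion.** The concern holds. As written, the confirmatory status of weight, SBP and hypoglycemia depends on which sentence is followed, and HbA1c superiority has no explicit rank. Keeping superiority outside the chain gives a one-sided error of about 0.047 at zero correlation, and 0.033 to 0.0475 over assumed correlations from −0.7 to 0.9, against 0.025. Using it as a gate controls error, but cuts the chance of reaching weight to between 2.5% and 96% for assumed true differences from 0 to −0.4, against 90% to over 99.9% on non-inferiority alone. The contradiction itself does not depend on these assumptions, and the primary non-inferiority claim is not affected. It must be resolved before unblinding.

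**What to change.** State one sequence in the synopsis, Protocol 9.1, 9.5.2 and 9.6, and SAP 8.1.1, 8.2 and 8.2.1, and record it in SAP 13. Either order below controls error; the sponsor should choose.

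1. **Non-inferiority, weight, SBP, hypoglycemia, HbA1c superiority.** This follows the order of the objectives. Add HbA1c superiority as the last step of every list. Make the upper-bound rule conditional on the three earlier secondary steps in the synopsis, Protocol 9.1 and 9.5.2, and SAP 8.1.1. Drop the clause in the synopsis and Protocol 9.1 that no further testing is needed. Delete both extra conditions in SAP 8.2.1. Cost: superiority waits on an SBP test in the subgroup with baseline SBP of at least 140 mmHg, for which no power is given; if an earlier step fails, the HbA1c interval is only descriptive as to superiority.
2. **Non-inferiority, HbA1c superiority, weight, SBP, hypoglycemia.** Keep the upper-bound rule and the SAP 8.2.1 conditions, and add HbA1c superiority as the first secondary step in every list. Cost: the other three secondaries become testable only with the superiority-gate probabilities shown above.

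In both cases, change the count in Protocol 9.6 from three to four, state one test level (one-sided 0.025, or two-sided 0.05 with claims only in the favourable direction), and make the weight condition in SAP 8.2.2 directional. These are wording changes with no effect on data collection or sample size.
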